In the combination portion of the study, Cycle 1 through Cycle 6, doxorubicin will be administered at  $75\text{ mg/m}^2$  on Day 1 of each 21-day cycle. Doxorubicin should be administered through a free-flowing catheter at  $75\text{ mg/m}^2$  by intravenous infusion in less than 60 minutes. A maximum of six cycles of doxorubicin (18 weeks of treatment) is permitted. Required prophylaxis for emesis and cardioprotection, as well as guidelines for prophylaxis with G-CSF for prevention of febrile neutropenia, is described in [Section 5.2.1](#). In Cycle 1 through Cycle 6, following prophylaxis as described in [Section 5.2.1](#) for possible infusion-related reactions, TTI-621 will be administered by intravenous infusion over 120 minutes on Day 1 and Day 8 of each 21-day cycle. Beginning with Cycle 2, the infusion period may be reduced to 60 minutes at the Investigator's discretion if the patient has not experienced infusion-related reaction.

For the purposes of safety decisions that guide cohort expansion and considerations of TTI-621 dose adjustment in the dose escalation portion of the study, the dose-limiting toxicity safety evaluation period will consist of the 21-day Cycle 1. Subjects will be considered evaluable for dose-limiting toxicity (DLT) if they received doxorubicin on Day 1 of Cycle 1 and TTI-621 on Day 1 and Day 8 of Cycle 1. A patient who withdraws from the study during Cycle 1 in the absence of objective disease progression or DLT will be replaced. If a dose-limiting toxicity as defined in [Section 5.4](#) is encountered in one patient in the initial three patients in a dose cohort, three additional patients will be enrolled in accordance with the standard 3+3 study design. The maximum tolerated dose (MTD) for this study will be defined as the maximum evaluated TTI-621 dose level at which <33% of patients within a dose cohort experience dose-limiting toxicity when administered in combination with doxorubicin at  $75\text{ mg/m}^2$ . While three pre-defined TTI-621 dose levels are anticipated, intermediate dose levels may be

studied to more closely characterize the safety profile of TTI-621 in combination with doxorubicin.

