After three patients in a dose cohort, or six patients in an expanded dose cohort, complete the 21-day dose-limiting toxicity assessment period, the incidence of dose-limiting toxicity, treatment-related safety observations and other available data, such as pharmacokinetic data, will be reviewed by the Sponsor Medical Monitor, Sponsor and Investigators. If no patient in a three-patient cohort or no more than one patient in a six-patient dose cohort experiences treatment-related dose-limiting toxicity, the dose level will be deemed safe and dose escalation may proceed unless there are other unsuspected but concerning safety observations that suggest either an expansion of the current dose level or implementation of an intermediate dose level.

After completion of Cycle 6, doxorubicin will be discontinued as per standard of care to avoid development of cumulative cardiac toxicity. Thereafter, beginning with Cycle 7, TTI-621 will be administered as monotherapy on Day 1 and Day 15 of 28-day cycles until documentation of disease progression or unacceptable toxicity.

Objective disease assessments will be performed after every second cycle of treatment for approximately 50 weeks and after every third cycle thereafter. A patient enrolled in an expansion cohort who withdraws or is withdrawn from the study prior to completion of two cycles of treatment and objective disease assessment after the second cycle for a reason other than disease progression or safety will be replaced in order to meet the statistical criteria for the Simon two-stage study design. Patients who withdraw from the study without objective evidence of disease progression will be followed until documentation of disease progression or initiation of another treatment. All patients will be followed in the Long-Term Follow-Up period for survival.

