#### 5.4. Dose-Limiting Toxicity Criteria for the Dose Escalation Portion of the Study

Dose-limiting toxicity is defined as any of the following treatment-emergent adverse events that occurs during the 21-day Cycle 1 and that are judged by the Investigator as related to TTI-621 or the combination of TTI-621 and doxorubicin. Adverse events that are in the opinion of the Investigator attributable exclusively to intravenous infusion of doxorubicin or any doxorubicin prophylaxis medication will not be considered a dose-limiting toxicity.

CCI

CCI

Infusion-related reactions with TTI-621 are not unexpected and prophylaxis guidelines are provided in [Section 5.2.1.2](#) to mitigate their occurrence and/or severity. While the Investigator may decrease the duration of TTI-621 infusion and/or may decrease or eliminate the steroid component of TTI-621 prophylaxis in a patient who has not experienced infusion-related reaction, caution is urged with respect to implementing both changes simultaneously and a stepwise approach is recommended.

In the event that one patient in a cohort of three patients experiences a dose-limiting toxicity, the cohort will be expanded to a total of six patients. If at least two patients within a dose cohort experience a dose-limiting toxicity during the dose-limiting toxicity period, the conclusion may be drawn that the maximum tolerated dose of TTI-621 in combination with 75 mg/m^2 doxorubicin has been exceeded; any further dose escalation, de-escalation or cohort expansion will be decided in consultation between Investigators, the Sponsor Medical Monitor and the Sponsor after consideration of the particular patients and adverse events experienced, as well as all available safety and pharmacokinetic data of all cohorts.

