$50 \times 10^9 – 25 \times 10^9/L$	
 
Omit TTI-621 on Day 8
 
Monitor platelet recovery (CBC twice weekly recommended)
 
Consider platelet transfusion per ASCO guidelines if clinically indicated
 
On Day 1 of next cycle: 
 
if platelets have recovered to <math>\geq 75 \times 10^9/L</math>, initiate cycle with doxorubicin at the same dose and TTI-621 at one dose level reduction
 
if platelets have not recovered to <math>\geq 75 \times 10^9/L</math>, hold doxorubicin and TTI-621 and monitor platelets; initiate the cycle when platelets recover to <math>\geq 75 \times 10^9/L</math> with doxorubicin at same dose and TTI-621 at one dose level reduction
 
 
 
In the case of a second occurrence of platelet count decrease to <math><50 \times 10^9</math>, follow the guidelines above or consult with the Sponsor Medical Monitor regarding management
 
The reduced dose of TTI-621 should be used for the remaining combination cycles
 
When the subject completes the combination portion of the study and moves to TTI-621 monotherapy: 
 
the original TTI-621 dose level should be re-instated and platelet counts monitored
 
in the case of platelets <math>< 50 \times 10^9/L</math> without other causality on Day 15, hold TTI-621 until platelets are <math>\geq 50 \times 10^9/L</math> and then continue with TTI-621 at a one dose level reduction
 
on second occurrence of platelets <math>< 50 \times 10^9/L</math> without other causality, reduce TTI-621 by an additional dose level and monitor for tolerability or consult with the sponsor medical monitor regarding management
 
in the absence of disease progression, further dose reductions may be implemented after discussion with the sponsor medical monitor
 
 
 

Platelet Count on Day 8	Management Guidelines

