### 12.2. Analysis Populations

The following analysis populations are defined for the study:

**Safety population:** all patients who received at least 1 dose of TTI-621

**Efficacy population:** all patients who received at least 1 dose of TTI-621

**DLT-evaluable population:** all patients who received the full dose of doxorubicin and the planned doses of TTI-621 on Day 1 and Day 8 and have been followed for the entire 21-day DLT period (i.e., Cycle 1) or who have a DLT during Cycle 1 will be considered DLT-evaluable

**Response-evaluation population for Simon two-stage design:** all patients in either Expansion Cohort A (low dose TTI-621) or Expansion Cohort B (high dose TTI-621) who complete at least two cycles of treatment as described in the protocol and have a post-treatment objective disease assessment unless they were withdrawn prior to meeting this criterion for safety or earlier demonstration of objective disease progression

**CCI** [REDACTED]: all patients who received at least one dose of TTI-621 and have at least one evaluable blood sample for analysis collected

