### 6.7.3 DLT-Evaluable Set (DES)

The DES is applicable to dose-escalation cohorts only. It will include patients who received the full dose of doxorubicin in Cycle 1 Day 1 and the planned doses of PF-07901800 on Day 1 and Day 8, and

Pfizer Inc. / Protocol: TTI-621-03/C4961003  
IQVIA Biotech (Confidential) Project # YXA42460

have been followed for the entire 21-day DLT period (Cycle 1) or who have a DLT during Cycle 1.

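### The dose-escalation rules define, replace and count DLT patients on different bases, so read literally a dose could pass with fewer than three DLT-evaluable patients

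*Protocol*

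**What the plan says.** **Evaluability.** The Protocol synopsis (Study Design) calls patients "evaluable for dose-limiting toxicity (DLT) if they received doxorubicin on Day 1 of Cycle 1 and TTI-621 on Day 1 and Day 8", both days falling in the first cycle, and Section 5.1 gives the same rule. Section 12.2 asks for the same dosing and adds an alternative: patients who "have been followed for the entire 21-day DLT period (i.e., Cycle 1) or who have a DLT during Cycle 1 will be considered DLT-evaluable". SAP 6.7.3 agrees with 12.2: patients who "have been followed for the entire 21-day DLT period (Cycle 1) or who have a DLT during Cycle 1". The synopsis and 5.1 do not contain the alternative of having a DLT. SAP 9.2 goes the other way and defines a DLT only in patients who had the full doxorubicin dose, both planned TTI-621 doses and the whole 21-day follow-up.

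**Replacement.** The synopsis states: "A patient who withdraws from the study during Cycle 1 in the absence of objective disease progression or DLT will be replaced". Section 5.1 repeats it. No other replacement rule is given for escalation patients.

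**Decision.** The cohort review takes place once three patients, or six in an expanded cohort, have finished the 21-day period (synopsis and 5.1; the synopsis cohort-assignment guidelines and 7.2 use the same trigger). The pass rule begins: "If no patient in a three-patient cohort or no more than one patient in a six-patient dose cohort experiences treatment-related dose-limiting toxicity". None of these passages says that the three or six must be DLT-evaluable.

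**Day 8 omission.** For platelets from 25 to 50 x 10^9/L, and again below 25 x 10^9/L, Table 22 in Section 9.5 says "Omit TTI-621 on Day 8". With clinically relevant bleeding the Day 8 dose is held. In each case the patient goes on to the next cycle once the stated conditions are met.

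**Two or more DLTs.** The synopsis defines the MTD by a DLT proportion below 33%. Section 5.4 says that with at least two DLTs "the conclusion may be drawn that the maximum tolerated dose of TTI-621" has been exceeded, and leaves further escalation, de-escalation or cohort expansion to consultation.

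**The concern.** A 3+3 design rests on very few patients, so who counts as one of them matters. Here three rules that should share a denominator do not: who is evaluable, who is replaced, and who is counted when a dose is judged.

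The patient caught between them is one whose Day 8 TTI-621 dose is omitted under Table 22, who meets no DLT criterion and who stays on study. That patient is outside the DLT-evaluable set, falls outside the replacement rule because there was no withdrawal, and still finishes the 21 days. A dose could then be judged with less information about the planned Cycle 1 exposure than three patients should give, and the information is lost in patients who could not receive that exposure.

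A second inconsistency concerns a patient whose toxicity both qualifies as a DLT and prevents the Day 8 dose. SAP 6.7.3 includes this patient because of the DLT. Read literally, SAP 9.2 does not count the event as a DLT, because the patient was not fully dosed.

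**Working it through.** **1. The plan's own figures.** Three dose levels of three patients give 3 x 3 = 9, and of six patients 3 x 6 = 18. This reproduces the stated range of nine to 18 (synopsis, Statistical Considerations; Protocol 12.1.1). The pass rule also agrees with the MTD threshold: 1/6 = 16.7% is below 33%, while 2/6 = 33.3% and 2/3 = 66.7% are not. The permissive wording in 5.4 therefore sits beside two other statements under which two DLTs in three or six patients do not meet the criterion.

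**2. One patient under each rule.** Take a patient with Day 8 omitted under Table 22, no DLT, still on study at Day 21.

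| Rule | Result |
|---|---|
| Synopsis and 5.1, evaluability | Not evaluable: no Day 8 dose |
| 12.2 and SAP 6.7.3 | Not evaluable: no Day 8 dose and no DLT |
| Replacement (synopsis, 5.1) | Not replaced: did not withdraw |
| Review trigger (synopsis, 5.1, 7.2) | Has finished 21 days, so can count |

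Now let the same patient have a DLT that prevents Day 8. Section 12.2 and SAP 6.7.3 make the patient evaluable, the synopsis and 5.1 do not, and SAP 9.2 does not recognise the event as a DLT.

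**3. Effect on a first cohort.** Let p be the true DLT rate with full Cycle 1 exposure. With three fully informative patients, P(no DLT) = (1 - p)^3. If the third patient could show no DLT at all, it is (1 - p)^2, which is an upper bound.

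| p | Three: (1 - p)^3 | Two: (1 - p)^2 |
|---|---|---|
| 0.20 | 0.512 | 0.640 |
| 0.33 | 0.301 | 0.449 |
| 0.40 | 0.216 | 0.360 |

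If the third patient's DLT risk is a fraction f of p, then P(no DLT) = (1 - p)^2 x (1 - f x p). At p = 0.33 and f = 0.5 (illustrative) this is 0.449 x 0.835 = 0.375, between the two ends.

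**4. Effect on the whole 3+3 step.** With full information, P(pass) = (1 - p)^3 + 3p(1 - p)^2 x (1 - p)^3. At p = 0.33: 0.301 + 0.445 x 0.301 = 0.434. With two informative patients in the first cohort and three in the second, P(pass) = (1 - p)^2 + 2p(1 - p) x (1 - p)^3. At p = 0.33: 0.449 + 0.442 x 0.301 = 0.582, again an upper bound.

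**5. How often it could happen.** The documents give no rate of Day 8 omission without a DLT, so this is an assumed range. With rate q per patient, the chance that at least one of three is affected is 1 - (1 - q)^3: 0.143, 0.271, 0.488 and 0.561 for q = 5%, 10%, 20% and 24%. The 24% is the rate of treatment-related Grade 3 or higher thrombocytopenia at 0.5 to 2.0 mg/kg in study TTI-621-01 (Protocol 3.7.1). It serves only as a high illustration, since that section describes the event as resolving by the next weekly infusion.

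**The case against.** The strongest reply is that the evaluability definition is introduced in the synopsis for the very purpose of the escalation decisions, so the three and six can sensibly be read as evaluable patients. That reading is reasonable, but it is not written down. The decision sentences use completion of the 21 days, and no sentence replaces a non-evaluable patient who stays on study.

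The redacted DLT list in 5.4 may capture many toxicity-driven omissions. Under 12.2 and SAP 6.7.3 those patients would be evaluable, and a DLT in one of the first three would expand the cohort. This narrows the gap by an unknown amount. It does not settle the conflict between SAP 6.7.3 and SAP 9.2.

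The third patient received both drugs on Day 1 and can still show a DLT, so the two-patient figures are bounds and not estimates. The cohort review also weighs other safety and pharmacokinetic data and may choose expansion or an intermediate dose. That is a real safeguard, but it does not define a denominator.

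A reader might infer more than the documents support:

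- That 2.0 mg/kg was passed on too few patients, and that this explains the closure of Cohort B. SAP 4.3.2 reports Grade 3 or 4 thrombocytopenia on Day 8 in expansion, during combination therapy. It does not confine this to Cycle 1 and does not show that any escalation patient was miscounted.
- That patients who leave in Cycle 1 for progression help a dose to pass. They are not replaced under the stated rule, but they do not finish the 21 days and so cannot be among the three.
- That a cohort with two DLTs in six could be enlarged until the proportion falls below 33%. The pass rule allows only none of three or at most one of six.

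Finally, SAP 9.1 already summarises omitted doses by treatment group and lists reasons for missed doses, so part of the reporting exists.

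**Conclusion.** The counting rules should be aligned. The text supports three findings: evaluability, replacement and the escalation decision use different bases; the sources disagree on whether a DLT that prevents the Day 8 dose counts; and the wording in 5.4 for two or more DLTs is looser than the MTD definition and the pass rule.

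That a non-evaluable patient can count towards the three is the literal reading, not an express rule. It depends on a Day 8 omission that meets no criterion in the redacted list. If it occurs in a first cohort, P(no DLT) at a true rate of 33% lies between 0.30 and 0.45, and P(pass) over the whole step lies between 0.43 and 0.58. The upper ends assume that the affected patient could not have shown a DLT. The documents do not show that it occurred in this trial.

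**What to change.** 1. In the Protocol synopsis, 5.1, 5.4 and 7.2, state that the three and the six in every escalation decision are DLT-evaluable patients as defined in 12.2.
2. Replace any escalation patient without a DLT who is not DLT-evaluable, whatever the reason.
3. Bring the synopsis, 5.1 and SAP 9.2 into line with 12.2 and SAP 6.7.3, so that a DLT that prevents the Day 8 dose is counted.
4. Reconcile the wording in 5.4 for two or more DLTs with the MTD definition and the pass rule, so that the same count leads to the same conclusion.
5. SAP 4.3.2 describes Stage 1 enrolment in Cohort B as complete, so escalation has probably ended. In that case make the SAP part of item 3, and add to the DLT table the number of non-evaluable patients at each dose, with the reason.

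The cost is a few sentences and one table row, plus possibly a few replacement patients if escalation is still open. Table 22, the doses and the clinical thresholds stay as they are.

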Reference Product Doxorubicin	
Doxorubicin is considered standard of care in the intended patient population and will be used in accordance with standard of care with intravenous infusion at a dose of 75 mg/m^2 on Day 1 of each 21-day cycle for a maximum of six cycles (18 weeks). Doxorubicin should be made up to a volume of 100 mL and administered through a free-flowing catheter at 75 mg/m^2 by intravenous infusion in less than 60 minutes. The rate of infusion should be decreased if erythematous streaking along the vein proximal to the site of infusion or facial flushing occur. Doxorubicin is emetogenic and prophylaxis for emesis prior to each infusion of doxorubicin should be given. Institutional guidelines for effective prophylaxis, including specific agents, additional agents and regimens, are acceptable. Cardioprotective prophylaxis must be implemented no later than with initiation of Cycle 5.
 
ASCO guidelines for use of WBC growth factors provide that 'prophylactic use of WBC growth factors for prevention of febrile neutropenia is warranted when the risk of febrile neutropenia is approximately 20% or higher and no other equally effective and safe regimen that does not require CSFs is available. Primary prophylaxis is recommended for the prevention of febrile neutropenia in patients who are at high risk on the basis of age, medical history, disease characteristics, and myelotoxicity of the chemotherapy regimen. The NCCN guidelines for hematopoietic growth factors classify soft tissue sarcoma treated with doxorubicin as an example of disease setting and chemotherapy regimen with a

	
high risk for febrile neutropenia (>20%) and recommends G-CSF prophylaxis for patients with high risk (>20%) of febrile neutropenia.
 
Thus, all patients receiving TTI-621 in combination with doxorubicin should receive prophylaxis with G-CSFs for prevention of febrile neutropenia. Suggested prophylaxis is pegfilgrastim and discussion with the Sponsor Medical Monitor is encouraged.
 
The Single Reference Safety Document (SRSD) for doxorubicin is the US Product Insert (USPI).

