In the combination portion of the study, Cycle 1 through Cycle 6, doxorubicin will be administered after emesis prophylaxis at  $75 \text{ mg/m}^2$  on Day 1 of each 21-day Cycle. It is intended that each patient will receive six cycles of doxorubicin as fewer than six cycles provides less benefit to the patient compared to six or more cycles and guidelines for prophylaxis for prevention of doxorubicin-mediated dose-limiting neutropenia are provided in [Section 5.2.1](#). Doxorubicin is administered through a free-flowing intravenous catheter in a volume of 100 mL by infusion over less than 60 minutes; prophylaxis for emesis should be given prior to each infusion and the site may follow institutional guidelines for prophylaxis and infusion as long as they do not contradict this requirement. The rate of infusion should be decreased if erythematous streaking along the vein proximal to the site of infusion or facial flushing occur. As described in [Section 5.2.1.1](#), prophylaxis with dexrazoxane for cardiotoxicity will begin no later than with initiation of Cycle 5 when cumulative doxorubicin will have reached  $300 \text{ mg/m}^2$ . Because of the potential for cumulative cardiac toxicity, a maximum of six cycles of doxorubicin (18 weeks of treatment) is permitted as per standard of care.

In Cycle 1 through Cycle 6, TTI-621 will be administered by intravenous infusion over 120 minutes on Day 1 and Day 8 of each 21-day cycle. Patients will receive prophylaxis as described in [Section 5.2.1.2](#) on each day of TTI-621 infusion for prevention of possible infusion-related reactions. Beginning with Cycle 2, the infusion period may be reduced to 60 minutes at the investigator's discretion if the patient has not experienced infusion-related reaction. In any cycle in which doxorubicin and TTI-621 are administered on the same day, doxorubicin treatment will precede administration of TTI-621; TTI-621 prophylaxis may begin prior to initiation of doxorubicin administration at the Investigator's discretion.

For the purposes of safety decisions that guide cohort expansion and considerations of TTI-621 dose adjustment in the dose escalation portion of the study, the safety period will consist of the 21-day Cycle 1. Subjects will be considered evaluable for dose-limiting toxicity if they received doxorubicin on Day 1.

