### 5.2.2. Doxorubicin

Doxorubicin will be administered with prophylaxis as described in [Section 5.2.1.1](#). In Cycle 1 through Cycle 6, doxorubicin will be used in accordance with standard of care with intravenous infusion at a dose of 75 mg/m^2 on Day 1 of each 21-day cycle for a maximum of six cycles (18 weeks). It is intended that each patient will receive six cycles of doxorubicin as fewer than six cycles provides less benefit to the patient compared to six or more cycles and guidelines for prophylaxis for prevention of doxorubicin-mediated dose-limiting neutropenia are provided in [Section 5.2.1](#). Investigators should consult the approved doxorubicin hydrochloride package insert for complete prescribing information (including warnings, precautions, contra-indications, adverse reactions and dose modifications) and may follow institutional procedures for the administration of doxorubicin. Doxorubicin should be made up to a volume of 100 mL and administered through a free-flowing catheter at 75 mg/m^2 by intravenous infusion in less than 60 minutes. The rate of infusion should be decreased if erythematous streaking along the vein proximal to the site of infusion or facial flushing occur.

In any cycle in which doxorubicin and TTI-621 are administered on the same day, doxorubicin treatment will precede administration of TTI-621. A delay before initiation of TTI-621 is not mandated.

As described below in [Section 5.2.3](#), it is intended that after completion of the planned six cycles of doxorubicin treatment, patients will transition to TTI-621 monotherapy and continue on monotherapy until progression. Patients who are unable to complete the planned six cycles of doxorubicin treatment

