### **9.3.3.3. Extravasation and Tissue Necrosis Related to Doxorubicin Administration**

Extravasation of doxorubicin can result in severe local tissue injury manifesting as blistering, ulceration, and necrosis requiring wide excision of the affected area and skin grafting. When given via a peripheral venous line, infuse doxorubicin over 10 minutes or less to minimize the risk of thrombosis or perivenous extravasation. If signs or symptoms of extravasation occur, immediately terminate the injection or infusion. Extravasation may be present in patients who do not experience a stinging or burning sensation or when blood return is present on aspiration of the infusion needle. If extravasation is suspected, apply ice to the site intermittently for 15 minutes, 4 times a day for 3 days. If appropriate, administer dexrazoxane at the site of extravasation as soon as possible and within the first 6 hours after extravasation.

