- j Assessed objectively by CT, MRI or PET/CT; the method used at baseline should be used for the duration of patient participation. Performed every  $6 \pm 1$  week for the first 18 weeks (during combination treatment), every  $8 \pm 1$  week until Week 50 or patient has been on study for one year, and every  $12 \pm 2$  weeks thereafter. CR or PR should be confirmed by repeat assessment at least four weeks after initial observation; treatment can continue during the interval between initial observation and confirmation. In the event that a patient is removed from the study in the absence of radiologic disease progression, a radiologic disease assessment should be performed at the Safety Follow-Up Visit if not performed within the previous four weeks and disease status should be assessed during Long-Term Follow-Up until radiologic demonstration of progression or initiation of new anti-cancer therapy, whichever occurs first
- k Patient-reported health-related quality of life will be assessed with the EORTC QLQ-C30 tool on Day 1 of every cycle and at the Safety Follow-Up visit prior to initiation of study treatment or other study activities

- i Doxorubicin should be administered through a free-flowing catheter at 75 mg/m^2 by intravenous infusion in less than 60 minutes. Prophylaxis against emesis and for prevention of febrile neutropenia should be administered as described in [Section 5.2.1.1](#); additional prophylaxis in accordance with institutional guidelines is acceptable
- m Cardioprotective administration of [dexrazoxane](#) should be initiated no later than initiation of Cycle 5 unless earlier initiation is medically advised or standard of care at a particular institution
- n Prophylaxis as described in [Section 5.2.1.2](#) will be initiated at least 30-60 minutes prior to initiation of TTI-621 infusion. TTI-621 is administered intravenously over 2 hours. At the Investigator's discretion and in the absence of infusion-related reaction in prior cycles, duration of infusion may be reduced to 60 minutes beginning with Cycle 2. Patients should be observed for one hour after infusion with vital signs assessment in 30-minutes for signs of infusion-related reaction in Cycle 1; the observation period may be reduced at the Investigator's discretion in patients who tolerate the infusion well and do not experience infusion-related reaction.

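### The doxorubicin administration sections permit any infusion under 60 minutes by any venous route, while Section 9.3.3.3 limits a peripheral-line infusion to 10 minutes; the two are not linked, and the slowing instruction is not reconciled with the tighter limit

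*Protocol*

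**What the plan says.** **Administration text.** One duration, under 60 minutes, appears in seven places in the Protocol: the Synopsis (Study Design, and Reference Product Doxorubicin), Sections 3.7.2, 5.1, 5.2.2 and 8.3.2, and the doxorubicin footnote to Table 24. The Synopsis (Reference Product Doxorubicin) reads: "by intravenous infusion in less than 60 minutes. The rate of infusion should be decreased if erythematous streaking along the vein". Section 5.1 reads: "Doxorubicin is administered through a free-flowing intravenous catheter in a volume of 100 mL by infusion over less than 60 minutes". The Table 24 footnote reads: "by intravenous infusion in less than 60 minutes". All seven call for a free-flowing catheter; none says whether it is central or peripheral. None mentions Section 9.3.3.3.

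**Slowing instruction.** Five of the seven (Synopsis Reference Product, 3.7.2, 5.1, 5.2.2 and 8.3.2) also fix the volume at 100 mL and add: "The rate of infusion should be decreased if erythematous streaking along the vein proximal to the site of infusion or facial flushing occur". They give no maximum duration once the rate has been reduced.

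**Peripheral-line limit.** Section 9.3.3.3 says: "When given via a peripheral venous line, infuse doxorubicin over 10 minutes or less to minimize the risk of thrombosis or perivenous extravasation". For extravasation itself it says: "If signs or symptoms of extravasation occur, immediately terminate the injection or infusion".

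**Local practice.** Section 5.1 provides that "the site may follow institutional guidelines for prophylaxis and infusion as long as they do not contradict this requirement". Sections 3.7.2 and 5.2.2 send investigators to the package insert for full prescribing details and allow institutional procedures for administration.

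**The concern.** The only route-specific administration rule for doxorubicin sits in a section on managing a toxicity, whereas staff preparing and giving the drug would work from 5.2.2, 8.3.2 or the Schedule of Assessments. Someone reading only those places has no notice that a shorter limit applies to a peripheral line.

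Slowing is a separate difficulty. Reducing the rate lengthens the infusion, and 9.3.3.3 caps its length for a peripheral line. The Protocol does not say what to do when the two meet.

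Section 9.3.3.3 itself describes what the precaution guards against: severe local tissue injury that can require wide excision and skin grafting. Adverse events and treatment delays or discontinuations are also components of the safety endpoints (Sections 4.2 and 4.4). With up to 20 centers, sites could follow different infusion practices while each believed it was following the Protocol.

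**Working it through.** The plan states no figure to reproduce. The check compares the sections by case and then does simple arithmetic on duration.

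**Step 1. Duration by access route**

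| Access | Infusion time | Administration sections (under 60 min) | Section 9.3.3.3 (peripheral, 10 min or less) |
|---|---|---|---|
| Peripheral | 10 min or less | met | met |
| Peripheral | more than 10, under 60 min | met | **not met** |
| Central | under 60 min | met | does not apply |

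The problem is confined to the second row.

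**Step 2. Distance between the ceilings**

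Inputs: 100 mL (Synopsis Reference Product, 3.7.2, 5.1, 5.2.2, 8.3.2); 60 minutes (same sections); 10 minutes (9.3.3.3).

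Rate = volume / time.

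- At 60 minutes: 100 / 60 = 1.67 mL/min, or 100 mL/h.
- At 10 minutes: 100 / 10 = 10 mL/min, or 600 mL/h.
- Ratio: 60 / 10 = 6.

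This is a ratio of permitted limits, not a measured difference in practice.

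**Step 3. Effect of slowing on a peripheral infusion**

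Let T be the planned minutes, f the fraction of the volume given before slowing, and r the rate afterwards relative to the rate before. If the full volume is given:

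Total time = T × [f + (1 − f)/r].

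For any f below 1 and r below 1 the bracket exceeds 1, so an infusion planned for exactly 10 minutes always ends above 10. For shorter plans it depends on f and r. The documents give neither, so the values below are assumptions.

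| f | r | Bracket | Planned 10 min becomes | Planned 5 min becomes | Longest plan that stays within 10 min (10 / bracket) |
|---|---|---|---|---|---|
| 0.75 | 0.5 | 1.25 | 12.5 | 6.25 | 8.0 |
| 0.50 | 0.5 | 1.50 | 15.0 | 7.5 | 6.7 |
| 0.25 | 0.5 | 1.75 | 17.5 | 8.75 | 5.7 |
| 0.50 | 0.25 | 2.50 | 25.0 | 12.5 | 4.0 |

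Slowing can therefore be compatible with 9.3.3.3, but only with enough margin in the planned time, and the Protocol does not mention such a margin.

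**Step 4. Is there a rule of precedence?**

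None was found. Section 8.3.2 cross-refers to 5.2.1.1 for prophylaxis, not to 9.3.3.3. Table 20 (Section 9.3.3.7) also tells sites to slow or stop for Grade 1 or 2 doxorubicin infusion reactions, without mentioning the peripheral limit. Section 5.1 ties institutional infusion practice to its own requirement, which is the 60-minute one.

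**The case against.** The strongest reply is that the two durations do not contradict each other. Ten minutes or less lies inside under 60 minutes, so a peripheral infusion kept to 10 minutes meets every section. On this view the Protocol has a general ceiling and a narrower rule for one route, and 9.3.3.3 binds sites as much as 5.2.2 does. This stands as far as planned duration is concerned. A reader might infer that any site following the dosing sections breaks the extravasation precaution. The documents do not support that: the line must be peripheral and the infusion longer than 10 minutes.

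Second, the dosing text does not leave sites with the 60-minute figure alone. Sections 3.7.2 and 5.2.2 point to the package insert, including its warnings and precautions, and to institutional procedures. This also stands in part. It means a site could miss the peripheral limit, not that it will. The pointers do not state the limit, however.

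Third, the slowing conflict is conditional. As the working shows, a short planned infusion may stay within 10 minutes after slowing. Two stronger readings should be set aside. One treats streaking as proof of peripheral access; no section says so, and facial flushing, the other trigger, is not tied to the line. The other treats streaking as a sign of extravasation, which would set slowing against immediate termination; 9.3.3.3 does not list streaking as such a sign.

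What survives is that the administration text permits something 9.3.3.3 excludes, and that slowing cannot be squared with the limit when a peripheral infusion is planned at or near 10 minutes.

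**Conclusion.** The point holds in a limited form, as an inconsistency between sections on drug administration. It covers peripheral infusions of more than 10 but under 60 minutes, and peripheral infusions that slowing takes past 10 minutes. The second group includes every infusion planned for exactly 10 minutes, then slowed and given in full.

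Its size in practice cannot be determined. A reader might multiply about 80 patients by six cycles to get 480 infusions. That is a ceiling on all doxorubicin infusions if everyone enrolled completes six cycles, not a count of those affected. The documents do not give the share of infusions through a peripheral line or the durations used, so the affected number could be anything from zero up to that ceiling. They also give no rate of vein or extravasation events, so an effect on the safety results is possible but not shown.

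Sample size, error rates, the response endpoint and the analysis plan are not affected. The change is still worth making, because the subject is a tissue-injury precaution the Protocol itself sets out and the remedy is a matter of wording. Nothing here bears on which infusion time or slowing rule is clinically right.

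**What to change.** Reconcile the Synopsis (both places), Sections 3.7.2, 5.1, 5.2.2 and 8.3.2 and the Table 24 doxorubicin footnote with Section 9.3.3.3. The reconciled text should:

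- state the infusion time by venous access route, or state expressly that one time applies to all routes;
- say how the instruction to slow for streaking or facial flushing applies for each route, and which instruction governs when slowing would exceed a limit;
- use the same wording in each place, or cross-refer to a single governing section, and bring Table 20 into line.

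The sponsor's clinical team decides what the rule is.

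The cost is a wording amendment or a clarification letter to sites, with no change to data collection, sample size or analysis. SAP Section 4.3.2 describes enrollment into expansion Cohorts B and C in the past tense. If doxorubicin dosing is already complete, the clarification would serve mainly for interpreting vein and extravasation events and for any later protocol that reuses this text.
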